#### 8.4.2. Secondary SPRO Endpoints

The following secondary SPRO responder endpoints will be assessed:

- Percentage of responders at Weeks 12, 16, and 20, where responders is defined as "very satisfied" or "satisfied"
- Percentage of patients achieving a ≥ 2-point change from baseline in the SPRO scale at Weeks 12, 16, 20, and 24

In addition, the continuous secondary SPRO endpoint of change from baseline at Weeks 12, 16, 20, and 24 will be assessed with a MMRM. The model will include fixed factors for treatment group, study visit, and treatment by study visit interaction, with baseline SALT score and baseline SPRO score as covariates. Imputed SPRO values will not be used for the MMRM.

#### 8.4.3. Clinical Global Impression of Improvement (CGI-I)

The CGI-I will be assessed by the Investigator at Weeks 12, 16, 20, and 24. Compared to the patient's alopecia areata prior to treatment at baseline, the patient's current state of alopecia areata will be assessed according to the Investigator's perceived change. The Investigator may select one of seven numeric choices representing "Very Much Worse" to "Very Much Improved". To reduce variability, one rater should perform the CGI-I assessment for the patient for the duration of the study. An example of the CGI-I assessment can be found in Appendix 17.3.2 of the protocol.

The secondary CGI-I responder endpoint of percentage of responders (defined as "much improved" or "very much improved") at Weeks 12, 16, 20, and 24 will be assessed.

#### 8.4.4. Clinical Global Impression of Severity (CGI-S)

The CGI-S will be assessed by the Investigator and will consider the severity of the patient's alopecia areata at the time of assessment. The Investigator may select one of seven numeric choices representing "Among the most extreme hair loss" to "Normal, no hair loss". To reduce variability, one rater should perform the CGI-S assessment for the patient for the duration of the study. An example of the CGI-S assessment can be found in Appendix 17.3.1 of the protocol.

The continuous secondary endpoint of change from baseline in the CGI-S at Weeks 12, 16, 20, and 24 will be assessed with a MMRM. The model will include fixed factors for treatment group, study visit, and treatment by study visit interaction, with baseline SALT score and baseline CGI-S score as covariates.

#### 8.4.5. Patient Global Impression of Improvement (PGI-I)

The PGI-I will be assessed by the patient at Weeks 12, 16, 20, and 24. Compared to the patient's alopecia areata prior to treatment at baseline, the patient's current state of alopecia areata will be assessed according to his/her perceived change. The patient may select one of seven numeric choices representing "Very Much Worse" to "Very Much Improved". An example of the PGI-I assessment can be found in Appendix 17.3.4 of the protocol.

The secondary PGI-I responder endpoint of percentage of responders (defined as "much improved" or "very much improved") at Weeks 12, 16, 20, and 24 will be assessed.

#### 8.4.6. Patient Global Impression of Severity (PGI-S)

The PGI-S will be assessed by the patient and will consider the severity of his/her alopecia areata at the time of assessment. The patient may select one of seven numeric choices representing "Among the most extreme hair loss" to "Normal, no hair loss". An example of the PGI-S assessment can be found in Appendix 17.3.3 of the protocol.

The continuous secondary endpoint of change from baseline in the PGI-S at Weeks 12, 16, 20, and 24 will be assessed with a MMRM. The model will include fixed factors for treatment group, study visit, and treatment by study visit interaction, with baseline SALT score and baseline PGI-S score as covariates.

#### 8.4.7. Brigham Eyebrow Tool for Alopecia (BETA)

The BETA is a clinician-rated scale that assesses the total eyebrow hair present. The scale is used for each eyebrow in which the Individual Eyebrow Score is derived by assessment of density (D) x surface area (SA). An expert panel will perform central readings based on photographs of the eyebrows and will provide a score for each patient with eyebrow involvement. The BETA will be performed at Baseline, Week 12, and Week 24.

The continuous secondary endpoint of change from baseline in the BETA at Weeks 12 and 24 will be assessed with a MMRM. The model will include fixed factors for treatment group, study visit, and treatment by study visit interaction, with baseline SALT score and baseline BETA score as covariates.

#### 8.4.8. Brigham Eyelash Tool for Alopecia (BELA)

The BELA is a clinician-rated scale that assesses the total eyelash hair present. The scale is used for each eye in which the Total Eyelash Score is derived by assessment of density and distribution on the right and left eye. An expert panel will perform central readings based on photographs of the eyelashes and will provide a score for each patient with eyelash involvement. The BELA will be performed at Baseline, Week 12, and Week 24.

The continuous secondary endpoint of change from baseline in the BELA at Weeks 12 and 24 will be assessed with a MMRM. The model will include fixed factors for treatment group, study visit, and treatment by study visit interaction, with baseline SALT score and baseline BELA score as covariates.

#### 8.4.9. Quality of Hair Patient Reported Outcome (QPRO)

The QPRO questionnaire is a 4-item assessment which provides additional details on key attributes of patient hair and helps provide context to the SPRO response. Like the SPRO, the QPRO responses are on a scale of 1-5, where 1 = very satisfied, 2 = satisfied, 3 = neither satisfied nor dissatisfied, 4 = dissatisfied, and 5 = very dissatisfied. An example of the QPRO assessment can be found in Appendix 17.4.2 of the protocol.

The continuous secondary endpoints of change from baseline each individual item for QPRO at Weeks 12, 16, 20, and 24 will be assessed with a MMRM. The model will include fixed factors for treatment group, study visit, and treatment by study visit interaction, with baseline SALT score and baseline QPRO item score as covariates.

#### 8.4.10. Hospital Anxiety and Depression Scale (HADS)

The HADS is a 14-item measure designed to assess anxiety and depression symptoms in medical patients. Items are rated on a 4-point severity scale. The HADS produces two scales, one for anxiety (HADS–A) and one for depression (HADS–D). An example of the HADS assessment can be found in Appendix 17.5 of the protocol.

The continuous secondary endpoints of change from baseline in HADS-A at Week 24 and change from baseline in HADS-D at Week 24 will be assessed with an ANCOVA. The model will include fixed factors for treatment group with baseline SALT score and baseline HADS score (HADS-A or HADS-D as appropriate) as covariates.

#### 8.5. Other Endpoints

A KM plot of time to first instance of post-baseline SALT  $\leq 20$  will also be included. Patients who do not meet the responder criteria will be censored at treatment end date or 24 weeks if the treatment end date extends beyond 24 weeks. Stratified log-rank statistics will be computed by randomization strata for CTP-543 8mg v. placebo and CTP-543 12mg v. placebo separately. The p values will be displayed with the KM plot. These p values are descriptive and are not part of the hierarchy outlined in Section 8.1.4 (Figure 1).

No other efficacy endpoints are specified.

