## 8.3. Patient Withdrawal Criteria

For all patients, it is the intent that patients who discontinue study medication (at any time) for any reason will continue to be followed for all protocol-planned study visits through the completion of the 24-week treatment period, and will have all endpoints (including efficacy) collected accordingly.

The Investigator, Sponsor, or its designee may decide a patient should discontinue treatment at any time and for any reason. In addition, patients will discontinue randomized treatment if they:

- Experience an intolerable adverse event: such events include, but are not limited to, adverse events ≥ Grade 4\*, bone marrow-related events, a ≥ Grade 3\* cardiac event (\*CTCAE v5.0 criteria);
- Require a medication that is prohibited by the protocol. However, under certain circumstances, and in consultation with the Medical Monitor, short-term use of a prohibited medication may not necessitate withdrawal of treatment when its use is unlikely to unfavorably alter the risk-benefit of subject participation;
- In the opinion of the Investigator, have any medically appropriate reason;
- Become pregnant;
- Have a serious adverse event associated with a SARS-CoV-2 infection;
- The Investigator believes that further treatment is undesirable or the risk-benefit profile has become unfavorable.

Furthermore, dose interruptions lasting more than 21 days may require treatment discontinuation on a case by case basis following consultation with the Medical Monitor.

In addition, patients are free to withdraw from participation in the study at any time, for any reason, and without prejudice. The Investigator must withdraw any patient from the study if the patient withdraws consent and requests to stop participating in the study. Patients who withdraw or are withdrawn from the study will not be replaced.

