#### **12.4.2.** Efficacy

The primary analysis targets an effect of treatment (response rates at 24 weeks) among subjects given the opportunity for treatment who are dispensed study drug. The treatment policy strategy is used for the intercurrent event of discontinuation of study treatment (either temporarily or permanently) and so the response rates at 24 weeks are of interest, irrespective of continued therapy, in line with the intent-to-treat principle.

For the primary efficacy analysis and the key secondary efficacy analysis, a 0.025 (two-sided) alpha-level will be allocated to each dose for comparison with placebo to adjust for multiplicity of testing associated with two doses. Additional secondary endpoints will be tested in the following order (see Section 12.4.3) and be considered statistically significant and alpha-level protected if they (and all prior endpoints in the hierarchy for that dose versus placebo) achieve statistical significance at the 0.025 level of significance. Irrespective, nominal p-values will be provided. Testing will be performed only for the Treatment Period. Missing values will be handled as specified in Section 12.4.4.

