Results of statistical models (ie, least-squares means, confidence intervals, risk differences) will be rounded to one additional decimal place from the original data, or a maximum of two decimal places. Standard error will be reported to an additional level of precision. Results which cannot be determined will be displayed as "NA", "NE", or similar.

For tests of hypothesis of treatment group differences, the associated p-value will be reported. All p-values will be rounded to four decimal places after assignment of statistical significance; pvalues that round to 0.0000 or are reported by SAS as zero will be presented as "≤0.0001"; pvalues that round to 1 or are reported by SAS as 1 will be presented as ">0.9999". P-values which are significant at a 0.05, 0.025, 0.01, 0.001, or 0.0001 level will be marked with asterisks. P-values which cannot be determined will be displayed as "NA". P-values are descriptive for outcomes and analyses not included in the multiplicity algorithm.

Date of last dose is collected on the *Treatment Discontinuation/Completion* eCRF page. For patients with missing or partial date of last dose, the date of last dose (ie, treatment end date) will be imputed. Date of last dose will be imputed as follows:

- Derive the number of tablets taken at the last visit as the dispensed amount minus the returned amount. For treatment compliance (Section 7.3) and exposure (Section 9.2), if the returned amount is missing, it will be assumed that zero tablets were taken. Otherwise, it will be assumed that 60 tables were taken.
- An estimated date of possible last dose will be calculated by adding the number of tablets taken divided by 2 to the visit date associated with the last visit where drug accountability was collected.
- If there is a partial date of last dose, missing day will be imputed using the day from treatment start date, or the last day of the month if that month has fewer days than the treatment start month.
- Treatment end date will be the minimum of the partial date of last dose, calculated estimated date of possible last dose, and collected study discontinuation/completion date.

Summary tables and data listings:

- Unless otherwise specified, no preliminary rounding will be performed; rounding will only occur after analysis.
- Data from patients excluded from an analysis population will be presented in the data listings but will not be included in the calculation of summary statistics, where applicable.

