#### 8.2.1. Computation of the Primary Endpoint

The SALT is a measure of hair loss that quantifies the amount of scalp surface without hair in a pre-specified quadrant of the scalp (right side, top, left side, back), that is further summed after applying a quadrant-specific multiplier indicative of scalp surface area contribution, to provide an overall score of total hair loss. A total SALT score equal to 0% indicates complete hair growth. A total SALT score equal to 100% indicates complete hair loss. An example of the SALT assessment can be found in Appendix 17.2 of protocol. The overall total SALT score is calculated in the eCOA system and will not re-derived. SALT scores are considered missing if the overall total could not be calculated. The primary endpoint is derived by categorizing the individual overall SALT scores at Week 24 ( $\leq 20$  versus > 20).

A multiple imputation (MI) approach will be used to estimate missing SALT scores.

One hundred independent imputations will be done with SAS® PROC MI using the Fully Conditional Specification (FCS) regression method. The FCS method combines both the monotone and arbitrary missing data patterns into one procedure, imputing missing values with a sequential regression approach.

For the primary efficacy analysis, missing SALT scores will be imputed under a missing at random (MAR) assumption. This assumes that patients who have missing data would have similar SALT scores as other patients in their respective treatment arm who have complete data. Any missing post-baseline SALT scores will be imputed to better inform the estimates of Week 24 missing SALT scores. Patients who have discontinued treatment but remain on study will not have their SALT scores censored, but any arbitrary missing SALT scores after the patient discontinued treatment will be imputed in the same manner. Utilizing the FCS method, missing

SALT scores will be imputed in a sequential manner using regression models with baseline SALT score and the observed or imputed values of previous visits as covariates. Imputations will be implemented separately for each treatment under the assumption that different treatments may have distinct posterior distributions.

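### SAP 8.5 counts a first SALT ≤20 at any time but censors never-responders at last dose, so, read literally, the descriptive Kaplan–Meier response curves can only be biased upward

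*SAP*

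**What the plan says.** SAP 8.5 (Other Endpoints) plans "A KM plot of time to first instance of post-baseline SALT" of 20 or less. It places no on-treatment limit on that event. The censoring rule covers only patients who never reach it: "Patients who do not meet the responder criteria will be censored at treatment end date or 24 weeks", the latter applying when treatment runs past 24 weeks. SAP 4 equates treatment end date with date of last dose. Where that date is missing or partial, "the date of last dose (ie, treatment end date) will be imputed", in part from tablet counts.

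Stopping drug does not end SALT assessment. Protocol 8.3 states the intent that patients who stop study medication "will continue to be followed for all protocol-planned study visits through the completion of the 24-week treatment period", with efficacy endpoints collected. For the primary endpoint, SAP 8.2.1 keeps those data: "Patients who have discontinued treatment but remain on study will not have their SALT scores censored". Protocol 12.4.2 gives the primary analysis its strategy: "The treatment policy strategy is used for the intercurrent event of discontinuation of study treatment".

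SAP 8.5 shows stratified log-rank p-values on the plot and calls them descriptive and outside the testing hierarchy. SAP 13 repeats that status and gives no reason for the censoring rule.

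**The concern.** Take two patients who stop drug at Week 10 and attend every SALT visit to Week 24. One first reaches SALT ≤20 at Week 20. That patient stays at risk to Week 20 and counts as an event. The other never responds. That patient leaves the risk set at Week 10, although observed as a non-responder for 14 more weeks. Whether follow-up after the last dose is used therefore depends on the outcome, which violates the non-informative censoring that Kaplan–Meier and log-rank methods need.

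The resulting curve is neither a clean treatment-policy curve nor a clean on-treatment curve. It would appear beside a primary result built on treatment policy, and a reader would take the two to describe the same quantity.

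**Working it through.** **Plan figures.** The documents give no figure for this analysis. The inputs borrowed from Protocol 12.1 (40%, 26%, 9%; 110, 220, 110 patients; two-sided 0.025, so z = 2.2414) do reproduce the stated power with a continuity correction of 0.5 × (1/n1 + 1/n2) and pooled null variance:
- 12 mg: (0.3009 − 2.2414 × 0.0580)/0.0541 = 3.16, power 99.9% (stated >99%).
- 8 mg: (0.1632 − 2.2414 × 0.0470)/0.0402 = 1.44, power 92.5% (stated about 92%).

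**Direction.** The response curve is 1 − Π(1 − d/r), with d first responses and r patients at risk at each visit. Compared with censoring at last SALT, the SAP text leaves every d unchanged and lowers r by the never-responders who have already stopped. Each d/r is equal or larger, so the curve can only rise. It rises strictly whenever a never-responder who is still being assessed stops before a later response occurs.

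**Size.** This was simulated with 200,000 patients per setting, with SALT visits at Weeks 4 to 24. Assumptions, because the documents give no values:
- 5, 10 or 20% stop drug, uniformly over Days 15–154, and all are followed to Week 24.
- The response hazard after stopping is 0, 0.25, 0.5 or 1 times the on-treatment hazard.
- Cumulative share of responders by visit is 0, 5, 25, 50, 78 and 100%.
- 40/26/9% are treated as cumulative first-response rates without discontinuation, although the protocol states them as rates at Week 24.

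Week 24 estimates (%) with half hazard after stopping, on nominal visit days:

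| Arm, stopping | SAP text | Censor at last SALT | Difference | Events and censoring both end at treatment end |
|---|---|---|---|---|
| 12 mg, 10% | 41.05 | 38.50 | 2.55 | 39.92 |
| 8 mg, 10% | 26.83 | 25.06 | 1.77 | 25.96 |
| Placebo, 10% | 9.38 | 8.69 | 0.69 | 9.04 |
| 12 mg, 20% | 42.32 | 37.06 | 5.26 | 39.88 |
| 8 mg, 20% | 27.82 | 24.04 | 3.78 | 25.96 |
| Placebo, 20% | 9.80 | 8.36 | 1.44 | 9.03 |

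The 12 mg minus placebo gap at Week 24 widens from 38.50 − 8.69 = 29.8 to 41.05 − 9.38 = 31.7 points at 10% stopping. At 20% it widens from 37.06 − 8.36 = 28.7 to 42.32 − 9.80 = 32.5.

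Inflation in points against censoring at last SALT, over all four post-stop hazards:

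| Arm | 5% stop | 10% stop | 20% stop |
|---|---|---|---|
| 12 mg | 1.0–1.6 | 2.1–3.1 | 4.4–6.2 |
| 8 mg | 0.8–1.0 | 1.6–2.0 | 3.5–4.0 |
| Placebo | 0.3 | 0.7 | 1.4–1.5 |

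**If stoppers leave the study.** For 12 mg, 20% stopping and half hazard, the inflation is 5.3 points if all stay, 2.8 if half leave, about 1.1 if 80% leave and 0 if all leave.

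**Log-rank.** This was checked under no treatment effect (110 per arm, 26% response in both arms, post-stop hazard unchanged, unstratified test, all stoppers followed). Rejection at nominal 5% was about 4.9% with 20% stopping in both arms. It was about 7 to 7.5% with 10% versus 25% stopping, with the shift favouring the arm that stops more.

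**The 24-week cap.** 24 × 7 = 168 days. SAP Table 2 puts the Week 24 target at Day 169 (efficacy window 166–172), and the schedule allows ±2 days. If never-responders are censored at Day 168 and Week 24 responses are dated Day 169 or later, only responders remain at risk, d = r, and the curve jumps to 100%. This occurred in simulation with no discontinuation and a true rate of 40%. It also occurred when last dose was dated the day before the visit. It disappeared when both were dated to the same day. Counting elapsed days makes an on-target visit tie with the cap, but a visit on Day 170 or 171 still falls after it.

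**The case against.** The strongest reply is that SAP 8.5 never says responses after treatment end count. The sentence in SAP 8.2.1 that keeps post-discontinuation SALT scores concerns the primary endpoint. If on-treatment response was meant, the rule is ordinary on-treatment censoring with a clause missing. If nobody responds after stopping, the SAP text and a consistent on-treatment rule give the same curve. This stands as a limit on the claim. But the event as written has no such restriction, so a programmer following the text would count late responses. Either intent needs a change to the wording.

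The size is also open. Follow-up to Week 24 is an intent: patients can withdraw consent, Protocol 8.4 withdraws unblinded patients from the study, and Protocol 9.5 can withdraw users of prohibited medication. The upper figures need nearly all stoppers to stay.

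Three stronger readings are tempting but not supported:
- *The rule contradicts the protocol's treatment policy strategy.* Protocol 12.4.2 assigns that strategy to the primary analysis. No estimand is assigned to this plot, so the rule is inconsistent with the primary approach but breaks no stated one.
- *The p-values are biased in favour of the drug.* The documents do not say which arm will stop more. With equal stopping and no effect the test held its level. With unequal stopping the error favours the arm that stops more, which could be placebo.
- *Confirmatory results are at risk.* The primary and key secondary endpoints use multiple imputation with the Mantel–Haenszel risk difference and do not use this censoring rule.

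**Conclusion.** The point holds for the text as written. Outcome-dependent censoring raises the response curves, and that direction follows from the estimator without simulation. The size rests on assumed stopping rates, stopping times and post-stop response. With 5–20% stopping and complete follow-up it is about 1–6 points for 12 mg, 1–4 for 8 mg and 0.3–1.5 for placebo, falling towards 0 as stoppers leave the study. Measured against a consistent on-treatment rule, it ranges from 0 to about 4 points for 12 mg. The jump at the 24-week cap depends on date conventions that SAP 8.5 does not define. It is potentially the more visible error, since it can arise with no discontinuation at all.

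The consequence is limited to one descriptive plot and its descriptive p-values. The wording should still be corrected, because the plan states a rule that gives a wrong curve and the remedy is small.

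**What to change.** In SAP 8.5, use one window for events and censoring. To match the primary analysis: count the first SALT ≤20 at any post-baseline assessment through the Week 24 visit, whatever the treatment status; censor non-responders at their last SALT assessment up to and including the in-window Week 24 visit; and place all Week 24 events and censoring at the same nominal time point. This also replaces a last-dose date that may be imputed with an observed assessment date.

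If an on-treatment analysis is intended, state instead that responses after treatment end do not count and label the plot accordingly. The shared Week 24 time point is needed in that case too.

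The cost is one or two sentences and a line or two of code. No new data are needed, and the sample size and testing hierarchy do not change.
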